### 4.2 Exclusion Criteria

Any of the following is regarded as a criterion for exclusion from the study:

1. Active psychosis
2. Bipolar I disorder history or severe level of mania on CAT-MH ( $\geq 71$ )
3. Acute suicidality or self-injurious behavior or severe level of suicidality on CAT-SS ( $\geq 71$ )
4. Cognitive inability as demonstrated by both the inability to complete an informed consent assessment AND complete the Montreal Cognitive Assessment (MOCA-BLIND)  $< 16$  when given chances on two different days
5. Current participation in another experimental research study
6. Previous participation in an 8-week intensive Mindfulness-Based Intervention in past 3 years or participation in the MINDFUL-OBOT pilot study
7. Expected medical hospitalization in next 6 months
8. Expected incarceration in next 6 months

9. Substance use severity requiring likely inpatient treatment in opinion of principal investigator (e.g., severe alcohol withdrawal symptoms, severe benzodiazepine withdrawal symptoms, etc.).
10. Inability to participate in group intervention without disrupting group in opinion of principal investigator.

#### **4. 4.3 Study Enrollment Procedures**

##### **Participant Recruitment**

We will primarily recruit from 3 non-CHA affiliated sites who have established experience providing OBOT (Boston Medical Center (BMC), Lynn Community Health Center (LCHC), and North Shore Community Health (NSCH)), as well as 2 CHA affiliated sites with an existing partnership with CHA (CHA Revere, CHA Union Square), in addition to up to 50 different primary care sites in Massachusetts associated with the MA OBAT Training and Technical Assistance (TTA) network, OBAT sites in U.S. states approved by the IRB for recruitment, and via Facebook and Instagram advertisements. To ensure a rigorous design, we will refer to the study during recruitment as a “study comparing two group programs designed to help reduce stress, anxiety, and craving during recovery,” which would avoid the impact of expectation bias towards or against mindfulness.

Referral process is described below. Participants will be recruited through:

1. A color flyer describing the details of the study, given to site staff at primary care sites throughout U.S. states approved by the IRB for recruitment to distribute to patients.
2. Information about the study will be posted on the CHA Addictions and CHA CMC website after IRB approval of the patient flyer.
3. The MA OBAT Training and Technical Assistance program will send a provider flyer to all nurse care managers working in OBAT across the state of Massachusetts to distribute to prescribers. Providers will receive a provider version of this flyer which will help them identify patients who may be interested and eligible.
4. Patients will be given the study flyer by their providers and nurse care managers. Providers and nurse care managers will not recruit or consent patients to the study, but rather will have the flyer available for any patients prescribed BUP who may be interested. Providers will refer interested patients to the study staff via email ([[contact]](mailto:[contact])) and/or by completing a google form on the CHA CMC website. Providers will receive verbal consent from their patients to pass along their names, phone number,

and email address to study staff so that they may be contacted regarding their interest in the study. Clinicians will be asked to include their email, as well as the optimal method and time to reach the patient they are referring. The referring clinician will only be contacted by the study team regarding enrollment status (i.e., enrolled or not enrolled) once a patient has signed the ICF and consented to this contact. Patients will also be encouraged to contact study staff via email if they are interested in the study.

5. Advertisements will be distributed to potential participants via Facebook and Instagram advertising. All advertising management will be conducted through Facebook, which controls advertisement on both social media platforms. The text and images used in the advertisements will be the same across platforms unless otherwise specified. The research team will not specifically choose individuals or groups to see these advertisements. The ad dissemination process will be completely automated, and Facebook will use a proprietary algorithm to identify users to whom the advertisements will be displayed. Specifically, these advertisements will be targeted to Facebook and Instagram users between the ages of 18-65+ who live in U.S. states approved for recruitment. Facebook does not allow advertisers to specify target ages above 65 and the research team will instead screen out referred participants who are over the age of 70 during the initial phone pre-screening call. Facebook will not share any user information with the research team, and the research team will not be able to identify the specific Facebook and Instagram users to whom the advertisements are displayed. Individual users will have the ability to like and comment on the advertisements and to post the advertisements to their personal pages; however, this would be done at a user's own personal discretion and no incentives will be provided for liking or sharing the Facebook or Instagram ads for this study. Furthermore, to protect confidentiality, our research team will not track or record any information about specific Facebook or Instagram users who may like, comment on, or repost the study advertisements. All Facebook and Instagram advertisements will be advertised by Cambridge Health Alliance's official Instagram account, "cambhealthalliance".
6. The recruitment team will not communicate with group moderators, groups, or individuals on Facebook or Instagram. The advertisements will be run through Facebook and the recruitment team will not specifically choose individuals or groups to see the advertisement. The criteria specified during the advertisement creation will be used by Facebook's algorithm to determine who is able to view the ads.

7. The principal investigator will not recruit his own patients into the study, though recruitment coordinators and Co-Is will support patient recruitment at each site.
8. Google advertisements and bulk-mail advertisements to local catchment area will be used if recruitment is slower than expected. All advertisements will require IRB approval prior to use.
9. The study team will utilize contact information in the Helping to Enhance Addiction Recovery Database (HEARD). Only participants from the “Exploring the attitudes and experiences of patients engaged in buprenorphine treatment during the COVID-19 pandemic” study who indicated their interest in future research opportunities will be contacted. The HEARD database contains contact information for individuals with OUD prescribed Buprenorphine who have indicated a willingness to be contacted about future research opportunities. Participants who elect to provide contact information and indicate that they would like to be contacted about future research opportunities will have their contact information (email address and phone number) added to a confidential, password-protected database by a team member who is listed on both study rosters. This database will only contain email addresses and phone numbers, and it will not be connected in any way to other data collected as part of this investigation. Participants from the present Mindful-OBOT R33 study who have indicated a willingness to be contacted about future research opportunities in the phone pre-screening form or the ICF will also have their names, phone numbers and email addresses added to this database. The PI will seek IRB approval for use of this database in any future research. Contact information will be stored for a period of five years or until we receive a request to remove someone’s contact information from the database.

**Procedures for documentation of reasons for ineligibility and for non-participation of eligible candidates (e.g. Screening Log)**

Interested patients will be referred to the study by their medical provider or nurse care manager via email or phone. Referring providers or nurse care managers will be able to describe the study to patients and obtain verbal consent to share patient names and contact information directly with the study team for study coordinators to reach out. Patients may also hear about the study through Facebook, Instagram, google ads or bulk mail ads and will have the option to express interest to the study team through a google form created to collect contact information. Since we will be recruiting patients from different primary care sites across the region, a trained Research Coordinator (RC) will conduct 15-30 minute phone screens with each interested patient to assess their eligibility. Patients will verbally consent to the phone screen and will be read a statement of confidentiality (see phone screen script included in the application). This will protect patients from unnecessarily consenting to and enrolling in the study and completing

screening measures if there is an obvious reason for their ineligibility that emerges through the phone screen. Decisions on inclusion/exclusion will be made by the RC with support from the PI, CMC medical director, and MINDFUL-OBOT clinical director. The participant will also be asked to provide emergency contact information (name and phone number) for their buprenorphine prescriber (in the demographics survey), who the study team will reach out to provide more context surrounding emergencies or potentially life-threatening AEs involving the participant. If the participant meets inclusion and exclusion criteria, then the RC will contact the patient and suggest scheduling an online study screening and consent visit via zoom videoconferencing. If the participant is deemed ineligible to participate during this screen, their reason for ineligibility will be documented and all pre-screening data will be removed from the pre-screening database.

[figure not shown]
During this visit, the patient will be given a verbal overview of the key information related to the study by the research coordinator, and an opportunity to consent to enrollment via the electronic consent module in REDCap. Once a patient completes the consent process by scoring at least 90% on the online consent assessment and signs the electronic consent form through REDCap, he/she will be referred to as a “participant” in the study. However, if the patient is unable to score 90% or higher on the consent assessment, then the research coordinator will administer the Montreal Cognitive Assessment-Blind (MOCA-BLIND) online through zoom to assess for eligibility (a study comparing the MOCA administered via videoconference vs. in person did not generate significant differences in outcome between the two groups). If they pass the MOCA-BLIND, then they will be allowed to review the consent document again with the research coordinator and complete a new consent assessment. If the participant does NOT pass the consent assessment on the second attempt, then they will no longer be eligible to join the study. If they do not pass the MOCA-BLIND, then the screening visit is over, and they will be able to be assessed once more on another day (since substance use can temporarily increase psychiatric symptoms and impact cognitive performance). On another day the coordinator will meet with the patient via zoom videoconferencing to review the protocol highlights again with the interested patient and offer a second chance to complete the consent assessment and MOCA-BLIND. If the participant has a MOCA-BLIND score below 16 on two separate occasions or scores less than 90% on the consent assessment again, they will not be eligible. If both failures are considered to be potentially due to ongoing substance use, then they may be screened again after 30 days if there has been a clinically significant change in their substance use status based on the judgement of the Principal Investigator (for example, they stopped alcohol use or tapered off the illicit benzodiazepine use, etc.). Once they sign the consent, they will receive a baseline diagnostic assessment using CAT-MH to identify psychiatric diagnoses and risk factors, and a review with a clinician will be required if there is possible psychiatric exclusion. Participants will also complete the PROMIS-ASF and the PhenX Substance Abuse and Addiction Core toolkit.

During this screening process, all eligible participants will need to rate the level of scheduling accessibility of the study groups days and times for both M-ROCC and the control group times being offered. Scheduling acceptability for assigned group will also be used as a covariate in statistical analyses.

If the participant is not excluded based on diagnosis, then they will be scheduled to complete the baseline survey and behavioral measures. If the participant has exclusion criteria on diagnostic assessments or cannot complete baseline measures, then the participant will not be eligible for randomization. Since participants with opioid use disorder often have transient mental health symptoms or intoxication related to recent substance use, participants with transient symptoms related to recent substance use will be able to wait for a re-review of eligibility after 30 days.

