## **Screening Assessments (Consent and Screening Visit)**

After participant consent has been obtained, the research coordinator will provide the participant with a secure REDCap link to the PROMIS-ASF, and PhenX toolkit surveys, as well as a secure link to a screening CAT-MH survey, to evaluate for eligibility prior to proceeding with baseline assessments. The RC will also supervise an oral fluid test with the participant to assess for substance use. If the screening process suggests that the participant meets exclusion criteria or brings up other questions about eligibility, then the RC will contact the PI or clinical director to review the information and decide prior to proceeding to baseline assessments. If a participant's PROMIS-ASF T score is greater than 55 (Raw > 16), then the participant will be determined to have an anxiety disorder even if it was not previously diagnosed clinically.

Since participants with opioid use disorder often have transient mental health symptoms or intoxication related to recent substance use, participants with transient symptoms related to recent substance use may be able to wait for a re-review of eligibility after 30 days.

During this screening visit, all eligible participants will be asked to fill out a Scheduling Acceptability form to rate the level of acceptability of the available study group day and time for both M-ROCC and control group times at the site, asking on a 0-10 scale how much they will be able to attend the group times.

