### **Randomization**

We will randomize participants in a 1:1 ratio of M-ROCC arm to control arm. We will randomize participants in randomly selected blocks of 4, 6, or 8 in a 1:1 ratio.

Randomization will be conducted as follows:

- 1) Participants who complete baseline measures and have a scheduling acceptability form will be entered into the randomization database.
- 2) Upon final review of eligibility, eligible participants will be marked as ready for randomization in the study database, which will alert the data analyst by automated email generated by REDCap.
- 3) The data analyst will randomize participants who are ready using a randomly selected block size (4, 6 or 8) (1:M-ROCC; 1:Control) and will enter the randomization status into the Study Status spreadsheet which the research coordinators will have access to and is kept secure within the CHA G Suite system.
- 4) The research coordinator will call the participant by phone to let them know the date/time that they can start LDM/Control.

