9. CAT-DI
10. CAT-ANX
11. CAT-PSY
12. CAT-MANIA
13. CAT-SUD
14. CAT- PTSD
15. CAT-SDOH

## 9.6 Data Analyses

### **Primary Outcome:**

The **main primary outcome** is biochemically-confirmed illicit opioid abstinent periods (defined by a negative oral fluid test [negative for opiate, oxycodone, fentanyl, methadone] AND no self-reported illicit opioid use), during the final 12 weeks of the study (with 6 being the highest possible number of oral fluid tests during that time period).

Negative toxicology screens have been previously used to assess effectiveness of OUD treatment. We will use an intent-to-treat design to evaluate the extent to which M-ROCC impacts biochemically confirmed illicit opioid abstinence over 6 biweekly time periods during the final 12 weeks of the study, **using Generalized Estimating Equations (GEE)**, which accounts for the clustering of individual observations over time, with covariates. This analytic approach provides reliable estimates even when data are unbalanced. GEE is also robust against misspecifications of the working correlation matrix when specifying the correct dependent-variable distribution and canonical link function. The benefit of selecting the best correlation structure is the gains in efficiency. The Quasi-likelihood Under Independence Model Criterion (QIC) will be used to ensure the best fitting working correlation structure. **For dichotomous outcomes**, we will specify a binomial distribution and a logit link function, and robust standard errors clustered at the individual-level. For **missing data**, we will implement multiple imputation methods in Stata (mi procedure). This technique creates multiple complete datasets, imputes missing values using a probabilistic simulation method (e.g., chained equations),

analyzes each dataset, and uses standard rules to combine estimates and adjust standard errors for the uncertainty of imputation.

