**Montreal Cognitive Assessment - Blind (MOCA-BLIND):** The MOCA was designed as a rapid screening instrument for mild cognitive dysfunction. The MOCA-BLIND is comprised of the same tasks as the original MOCA, with visual elements removed. It assesses different cognitive domains: attention and concentration, memory, language, conceptual thinking, calculations, and orientation. The total possible score is 22 points; a score of 16 or above is considered normal in substance use disorder context. Duration: 10 min.

A brief **demographics survey** will note participant race, ethnicity, primary language, income, address (including the street, unit/apartment number if applicable, city, state, and zip code), phone number and e-mail address of three close contacts, Facebook

and Instagram handle, name and phone number of buprenorphine prescriber, and other quantifiable attributes. Duration: 4 min.

**Scheduling Acceptability Survey:** This survey will ask participants to rate, on a scale of 1-10, the likelihood that they can attend the day/time that the current control and LDM/MTPC groups are being held.

*Baseline Battery for Participants:*

**A Survey of Meditation and Mindfulness Experience (SMME)** will assess the participant's previous experience with meditation and Mindfulness-based interventions, both over their lifetime and in the past two weeks. This will be a brief questionnaire. Duration: 3 min.

**Adverse Childhood Experiences (ACE) Questionnaire:** The Adverse Childhood Experienced (ACE) Questionnaire is a 10-item self-report measure that identifies childhood experiences of physical, sexual, and emotional abuse; neglect by parents or caregivers; violence between parents or caregivers; other kinds of serious household dysfunction such as alcohol and substance abuse; and peer violence, witnessing community violence, and exposure to collective violence. Participants indicate "yes" or "no" to having experienced each type of ACE, and the score is calculated by summing up the number of questions to which they responded "yes." Duration: 4 min

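### Adjusting for the acceptability of the assigned group's time slot lets allocation choose the covariate, which can shift the intent-to-treat arm estimate

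*Combined protocol and SAP*

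**What the plan says.** Section 4.3 (Study Enrollment Procedures) asks all eligible participants to "rate the level of scheduling accessibility of the study groups days and times for both M-ROCC and the control group times being offered". The next sentence reads: "Scheduling acceptability for assigned group will also be used as a covariate in statistical analyses".

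The ratings precede allocation. Section 6.2.2 (Randomization) states: "Participants who complete baseline measures and have a scheduling acceptability form will be entered into the randomization database".

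Section 9.6 describes the primary GEE as a method "which accounts for the clustering of individual observations over time, with covariates" and does not list those covariates. The one explicit list there, for the retention analysis, covers diagnosis, demographics, treatment history and similar variables. It does not include scheduling acceptability.

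The rating scale is given in two ways. Section 6.2.2 (Screening Assessments) describes the form as "asking on a 0-10 scale how much they will be able to attend the group times". Section 10.1 describes it as rating "on a scale of 1-10, the likelihood that they can attend the day/time that the current control and LDM/MTPC groups are being held".

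**The concern.** Each of the two ratings is a proper baseline variable, and randomisation balances each of them. The variable that the plan enters is neither one. Write M for a person's M-ROCC rating, C for the control rating, and Z = 1 for M-ROCC. The covariate is A = Z·M + (1 − Z)·C, and allocation decides which rating it contains.

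If one arm's slot is on average easier to attend, A differs between arms by construction. Two people in different arms with the same value of A then differ in general availability. Comparing them at equal A undoes part of the balance that randomisation gave. At stake is the intent-to-treat contrast defined in 9.3 and promised in 9.6: the adjusted arm coefficient can be non-zero when M-ROCC has no effect.

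**Working it through.** **The plan's own figures, for scale (9.2).** The plan states no figure for the covariate adjustment. Its power inputs reproduce: design effect 1 + (24 − 1) × 0.01 = 1.23; 192 / 1.23 = 156.1, or 78 per arm; difference 4.67 − 4.11 = 0.56 periods; pooled SD √[(1.23² + 1.27²)/2] = 1.25; d = 0.56 / 1.25 = 0.448. Power at d = 0.45 with 78 per arm is 80.2% (normal) or 79.7% (t), in line with the stated figure. None of this depends on the covariate. It supplies the yardstick of 0.56 periods, or 0.45 SD.

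**Formula.** With no true arm effect, and outcome related to the ratings only through general availability, the expected arm coefficient after adjusting for A is

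bias = −b × (mean M − mean C),

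where b is the within-arm slope of outcome on A.

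**Assumptions (none is in the documents).** Correlation 0.5 between a person's two ratings; general availability correlated r = 0.2, 0.3 or 0.4 with outcome; the same slot gap in every cohort. In SD units b = r × √0.5.

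- Low corner (r = 0.2, gap 0.5 SD): 0.2 × 0.707 × 0.5 = 0.07 SD.
- High corner (r = 0.4, gap 1 SD): 0.4 × 0.707 × 1 = 0.28 SD.

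Approximate type I error with 192 randomised: SE² = (1 − b²) × (4/192) × (1 + gap²/4).

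- Low: SE = √(0.98 × 0.02083 × 1.0625) = 0.147; 0.071 / 0.147 = 0.48; two-sided rejection about 8%.
- High: SE = √(0.92 × 0.02083 × 1.25) = 0.155; 0.283 / 0.155 = 1.83; two-sided rejection about 45%.

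A null simulation with n = 192 over the same ranges gave 0.08 to 0.28 SD and 8% to 42%, close to these values.

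**Simulation in trial units.** 96 per arm, 4,000 null trials per cell, linear model on the 0–6 count, rating SD assumed 2.5 points, outcome SD 1.25. Entries are the spurious difference in periods and the type I error when adjusting for the assigned rating, for a more acceptable M-ROCC slot.

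| Gap (points) | r = 0.2 | r = 0.3 | r = 0.4 |
|---|---|---|---|
| 0 | 0; 4.9% | 0; 5.2% | 0; 5.4% |
| 1 | −0.07; 6.8% | −0.11; 8.9% | −0.14; 12.3% |
| 2 | −0.14; 10.9% | −0.21; 19.4% | −0.28; 32.7% |
| 3 | −0.21; 17.2% | −0.32; 33.7% | −0.42; 54.6% |

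In the same runs the unadjusted model rejected 4.6% to 5.4% of the time. The model with both ratings rejected 4.8% to 5.6%, with bias between −0.003 and 0.006 periods.

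**Logit GEE on six binary periods**, one assumed scenario, 300 runs per gap. At gaps of 1, 2 and 3 points, the assigned rating gave spurious odds ratios of 0.89, 0.76 and 0.66, with rejection of 10%, 28% and 51%. With both ratings, odds ratios were 0.99 to 1.01 and rejection 4% to 6%.

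**If slot convenience also acts on outcome directly.** Let it add c·A. The intent-to-treat contrast with no content effect is then c × gap, and the contrast with convenience removed is 0. Adjusting for A alone gives −r√0.5 × gap. When general availability also matters (r above 0), that equals neither target. For example, with c = 0.2, r = 0.3 and gap 1 SD, the targets are 0.20 and 0, and the planned model gives −0.21.

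**The case against.** Several counter-arguments have force.

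*The slots may not differ.* Both arms' times are rated, but no passage says that they are unequal in convenience. A reader might infer a systematic gap from the separate groups; the documents do not establish one. Section 5.1 (Administration) starts new groups every 4–5 weeks, so times could change. If the gap varies by cohort around zero, average bias is negligible (at most 0.007 SD in simulation) and type I error stays near nominal, about 5% to 6%, possibly slightly higher with very variable gaps. This stands: the larger figures need a gap in a consistent direction.

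*Direction.* A reader might infer that the adjustment always favours the arm with the less convenient slot. That holds only if higher ratings go with better outcomes. Free time may reflect unemployment, which 9.6 lists among factors affecting retention, and the sign could reverse.

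*Reach.* A reader might infer that the primary analysis is definitely affected. The sentence in 4.3 covers statistical analyses without limit, but 9.6 does not name the variable.

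*Purpose.* The comparator is meant to isolate mindfulness, so removing a scheduling difference is a defensible aim. If convenience acts only directly on outcome, adjusting for the assigned rating removes it correctly (bias about 0, type I error 5% to 6%), while the both-ratings and unadjusted models keep it in the contrast: 0.08 to 0.30 SD and 9% to 55% rejection at slopes of 0.15 to 0.30 and gaps of 0.5 to 1 SD. This is a choice of estimand, and the both-ratings model is not free of scheduling effects. It does not rescue the plan. The stated estimand is intent-to-treat, to which such an effect belongs, and the assigned rating alone misses both targets once general availability also predicts outcome.

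**Conclusion.** The concern holds in conditional form. The covariate as written is selected by allocation. It shifts the intent-to-treat estimate when two conditions hold together: the slots' mean ratings differ consistently, and the rating is associated with outcome within arm. Measuring both ratings before randomisation does not prevent this.

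The algebra is firm; the magnitude is not. The range of about 0.07 to 0.28 SD (0.09 to 0.35 periods at SD 1.25), with type I error from about 8% to a little over 40%, rests on the assumed gaps, correlations and a constant gap across cohorts. The documents cannot confirm that bias will occur, which arm it would favour, or that the primary model uses the covariate. It should be corrected because the rule is unsafe and a safe alternative is available from the same data.

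The mismatch between a 0–10 and a 1–10 scale is a separate wording error and adds nothing to the bias argument.

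**What to change.** 1. In 4.3, replace the sentence on the assigned group with: the two pre-randomisation ratings (M-ROCC slot and control slot) will both be entered for every participant, whatever the arm, in the intent-to-treat models. Entering neither is equally valid. State that any effect of slot convenience then remains in the arm contrast.
2. In 9.6, list the covariates of the primary GEE and of each secondary model, and say which models include these ratings.
3. If the effect with slot convenience removed is also wanted, add the assigned-slot rating alongside both ratings in a labelled sensitivity analysis, never on its own. With both ratings held fixed, allocation alone determines the assigned rating, so general availability no longer confounds it. This still assumes linear effects and no other interaction between arm and the difference in ratings.
4. Use one rating scale in 6.2.2 and 10.1, matching the form actually used.

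The cost is a few sentences and one extra degree of freedom. No new data are needed, because both ratings are already required before randomisation.
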